## 6. Research Plan:

The proposed study will enroll 5 NHB and 5 NHW catastrophizing participants with symptomatic knee OA. The study will over-enroll 3 additional participants due to attrition over the three-day study period. Up to 180 additional participants may undergo screening procedures and will count toward screen failures. Potential participants will undergo a standardized telephone or in-person screening which will include the pain catastrophizing questionnaire, as well as screening questions that inquire about conditions that are listed under our inclusion and exclusion criteria to confirm initial eligibility. Participants will be informed that if they do participate in this study, we will keep the information the participant provide in addition to information provided to these questions as part of this research study. If the participant does not meet inclusion criteria or decides not to participate in the study, the participant will be informed that no additional information would be collected, but any information up to that point would be maintained. Thirty potential participants will be screened to determine initial eligibility. Patients will be excluded if they have concurrent medical or arthritic conditions that could confound symptomatic knee OA related outcome measures or coexisting disease that could preclude successful completion of the protocol including: systemic rheumatic disease/condition, including rheumatoid arthritis, systemic lupus erythematosus, gout, and fibromyalgia; a history of clinically significant surgery to the index knee (e.g. open reconstruction, knee replacement or major surgery on one or both knees); uncontrolled hypertension ( $> 150/95$ ); loss of peripheral sensation in areas of the body that will be tested with QST; certain neurological diseases that could interfere with protocol completion such as s Parkinson's disease, multiple sclerosis, stroke with loss of sensory or motor function, or uncontrolled seizures; cardiovascular or peripheral arterial disease; serious psychiatric disorder requiring hospitalization within the past 12 months; diminished cognitive function that would interfere with completion of study procedures. Daily opioid use will also be an exclusion, as well as a Pain Catastrophizing Score of less than 10. Hospitalization within the preceding year for psychiatric illness, serious psychiatric disorder requiring hospitalization within the past 12 months or characterized by active suicidal ideation or diminished cognitive function that would interfere with completion of study procedures. Pregnancy will also be an exclusion. Also, contraindications to MRI scanning (e.g. presence of metal implants, claustrophobia) will be exclusion criteria. Any criteria for MRI Exclusion, such as the presence of non-removable metallic, magnetic material or devices such as pacemakers, aneurism clips, or claustrophobia, which could pose a risk for injury in the MRI scanner. The study will include questionnaires to assess pain, clinical symptoms, and pain catastrophizing. All questionnaires provided during this research study's timeline are shown in Table 2. Quantitative Sensory Testing (QST) will be performed at the Pain Clinical Research Unit (PainCRU), a fully equipped sensory testing lab within the UF Pain Research and Intervention Center of Excellence (PRICE) directed by [name] (mentor).

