**Randomization and General Procedures.** Individuals will be randomized to one of two groups (stratified by sex): 1) a 30-minute, single-session cognitive-behavioral intervention designed to reduce pain catastrophizing or 2) a control condition that receives pain education. Testing will occur on two days (Figure 1). On Day 1, participants will attend a laboratory session whereby informed consent will be reviewed; health, pain, and demographic history will be obtained and physical examination will be performed to identify the most symptomatic knee. Female participants of childbearing potential will complete a one-time pregnancy test at the beginning of the session on day one. Trait pain catastrophizing will be assessed prior to pain testing. Day 1 session is expected to last up to 1.5 hours. On Day 2, participants will undergo neuroimaging acquisition followed by assessment of State Pain Catastrophizing Scale (S-PCS) in response to the pain-evoked cerebral responses (see **neuroimaging protocol** above). Then, participants will complete QST assessment of responses to pressure (i.e., pressure pain threshold), and punctate mechanical stimuli (i.e., temporal summation of mechanical pain) in a laboratory session lasting 30-60 minutes. State Pain Catastrophizing Scale (S-PCS) will be assessed immediately after each pain induction procedure. There will be a 30-minute rest period between the neuroimaging and QST session. Day 2 session is expected to last 2.5 to 3 hours. On Day 3, each participant will receive either the cognitive-behavioral intervention or the pain education (control condition), followed by post-tests that will be identical to the pre-tests given on Day 2, except that participants in the pain catastrophizing reduction group will be told to use the coping strategies they learned. Once all testing is over, participants will be debriefed and provided with an honorarium. Day 3 testing session is expected to last 3 to 3.5 hours. Audio recording will be conducted at the end of the study in order to obtain feedback on what intervention techniques participants used and whether they noticed any difference during Day 3 testing. We will audio record responses to the following questions: 1) during this last testing, please tell us what you were able to do; 2) describe how you applied your techniques; 3) did you notice any difference in your reactions to the stimulations; and 4) what did you notice? Further, participants will be asked to rate on a scale from 0-10 how well they were able to use the strategies and how effective they felt the strategies were. These recording will be reviewed by the study team to assess the quality of our treatment visits. These recording will not be released and will only be accessible by study investigators. At the end of the study, the recordings will be transcribed and the audio recordings will be destroyed. State Pain Catastrophizing Scale (S-PCS) will be used as a manipulation check to verify that catastrophizing was effectively. **Pain Catastrophizing Reduction Group:** The cognitive-behavioral intervention will comprise three components: 1) general education about pain (e.g., pain pathways) and a rationale for the intervention (e.g., gate control theory); 2) impact of positive and negative pain-related thoughts on neural process of pain; and 3) a guided imaginal pain exposure exercise. We and others have successfully applied these and similar approaches to reducing pain catastrophizing [12; 13; 48; 49] (see manual for details). **Pain Education Group:** This group will receive general information about the neurobiology of pain and knee OA. At no time will they be taught about pain modulation or the interface of thoughts, feelings, and pain [48; 49].

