**Data Analysis.** Procedures will be put in place to ensure data integrity and the protection of subject identification. Data will be inspected for distributional form, missing values, and implausible values. We will compare data on study completers and those lost to follow-up to investigate potential biases. The assumption of normality will be checked using histograms and normal probability plots. The assumptions of regression and mediation models will be checked using residual plots and plots of influence statistics. All statistical analyses will be conducted with statistical software SAS version 9.4 (Cary, N.C.) and R version 3.2.2 (The R Foundation for Statistical Computing). All hypothesis testing conducted to address the primary aim (comparing ethnic groups on pain-related brain function, clinical pain, and pain sensitivity measures) will be two-sided with a Bonferroni corrected level of significance of .004 (.05 divided by 12 tests). Hypothesis testing using ANCOVA models will also be two-sided with a Bonferroni corrected level of significance of .004. We will control for SES and discrimination in all analyses.

We will use separate ANCOVA models to investigate the effect of the manipulation (the independent variable) on pain-related neural processes and pain measures. The measures at baseline are the covariates while the measures post-manipulation are the dependent variables. We will again use separate ANCOVA models which will include an ethnic group variable and an manipulation-ethnic group interaction term to test the hypothesis that the manipulation will produce differentiated pain-related brain responses due to ethnicity.

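### The single-step Bonferroni cut-off is valid, but Holm's step-down over a named family gives the same 5% control and can only gain power; the gain here is small for plausible effects and near nil for the interaction tests

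*Combined protocol and SAP*

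**What the plan says.** The rule is in Section 6 (Research Plan), under Data Analysis. Tests for the primary aim are to be "two-sided with a Bonferroni corrected level of significance of .004 (.05 divided by 12 tests"). That aim is described there as "comparing ethnic groups on pain-related brain function, clinical pain, and pain sensitivity measures". A second sentence extends the level: "Hypothesis testing using ANCOVA models will also be two-sided with a Bonferroni corrected level of significance of .004". No step-down, gatekeeping or other ordered procedure appears anywhere. The 12 tests are not listed, and the text does not say whether the ANCOVA tests are among them.

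Three other statements fix the setting. On size: "The proposed study will enroll 5 NHB and 5 NHW catastrophizing participants with symptomatic knee OA", with 3 more allowed for attrition. On covariates: "We will control for SES and discrimination in all analyses". The second set of ANCOVAs adds "an ethnic group variable and an manipulation-ethnic group interaction term"; these are the models that bear on Hypotheses 1a and 1b. The documents give no expected effect size, no correlation between outcomes and no power calculation.

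**The concern.** Under a single-step rule every test must reach .004, however many others have already been rejected. Holm orders the p-values and compares the smallest with .05/12, the next with .05/11, and so on up to .05, stopping at the first failure. It needs no assumption beyond Bonferroni's.

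Specific Aim 1 expects one manipulation to move experimental pain, clinical pain and brain responses together. Several true effects at once is the case in which a single-step rule gives up most power. With 10 planned completers, power gained without an extra participant is worth having. What is at stake is how many outcomes can be declared after the first one, not whether false positives are controlled.

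**Working it through.** **1. The plan's figure.** .05/12 = .004167, which is .004 to three decimals. At .004 the family-wise bound for 12 tests is 12 × .004 = .048. The figure reproduces and is slightly conservative.

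**2. Holm's cut-offs.** .05/(12 − i) for i = 0 to 11 gives .00417, .00455, .00500, .00556, .00625, .00714, .00833, .01000, .01250, .01667, .02500, .05000. The first equals .05/12, so the chance of at least one rejection is the same as under Bonferroni at .05/12. Every later cut-off is larger, so nothing that Bonferroni rejects is lost.

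**3. Error control.** Holm's 5% bound holds under any dependence. Simulation with 6 true nulls, 6 very large effects and 5 df gave a family-wise error of .047 to .049 for Holm and .025 for Bonferroni. Both are within .05.

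**4. Error df with 10 completers**, counting 1 df each for SES and discrimination (assumed):
- adjusted ethnic comparison: intercept, ethnicity, SES, discrimination; 10 − 4 = 6
- manipulation ANCOVA: intercept, manipulation, baseline, SES, discrimination; 10 − 5 = 5
- interaction ANCOVA: intercept, manipulation, ethnicity, interaction, baseline, SES, discrimination; 10 − 7 = 3

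At 3 df the critical |t| is 7.94 for the first test under either method and 7.70 for Holm's second.

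**5. Power.** For 5 against 5 the standard error of the contrast is √(1/5 + 1/5) = 0.632 SD, so an effect of 2 SD has noncentrality 2/0.632 = 3.16. For the interaction, with assumed cells of 2, 3, 2 and 3, it is √(1/2 + 1/3 + 1/2 + 1/3) = 1.29 SD, so 2 SD has noncentrality 2/1.29 = 1.55. Covariates are taken as unrelated to group; any relation would lower these values. Bonferroni power follows from the noncentral t distribution and Holm power from simulated sets of 12 t-statistics, with assumed correlation 0.3 and all 12 outcomes affected.

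Average power per test, Bonferroni to Holm:

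| Effect | Manipulation ANCOVA, 5 df | Interaction ANCOVA, 3 df |
|---|---|---|
| 1 SD | 3.5% to 3.7% | 0.8% to 0.8% |
| 1.5 SD | 9% to 11% | 1.3% to 1.3% |
| 2 SD | 20% to 26% | 2.1% to 2.2% |
| 3 SD | 52% to 77% | 4.6% to 4.9% |

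For the adjusted ethnic comparison (6 df) the figure at 2 SD is about 24% to 33%. If only 6 of the 12 outcomes are affected at 2 SD, the 5-df gain shrinks to 20% to 22%. Holm rejects strictly more hypotheses in about a third of simulated trials at 2 SD with 5 df, but in under 1% for the interaction at 2 SD.

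**6. Family.** If Holm at .05 is written separately into both sentences and the two sets of tests differ, the overall bound is .05 + .05 = .10. The present text has a similar ambiguity: if the ANCOVA tests are additional, the bound at .004 is 24 × .004 = .096 for 24 tests and 36 × .004 = .144 for 36 (both counts are assumptions).

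**The case against.** The strongest reply is that nothing is wrong. Bonferroni is valid, prespecified and correctly computed, and choosing between two valid methods is partly preference. That stands, and it limits the point to an optional gain.

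A second reply is that the gain misses the main hypotheses. Hypotheses 1a and 1b rest on the interaction, where the models leave 3 df and Holm changes almost nothing. That also stands. The gain concerns the manipulation and ethnic-group contrasts, and there only if effects are large and widespread.

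A third is that Holm must rank all p-values in a defined family, whereas a fixed .004 can be applied test by test. This is right as a condition on the fix. It does not favour the present text, because a divisor of 12 also presupposes a known family.

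A fourth is that a study meant to supply preliminary data needs estimates and intervals, which Holm makes less direct. This is a real but small cost.

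A reader might infer a larger benefit from an unadjusted 5-against-5 t-test with 8 df, where 2 SD gives 32% to 42% and 3 SD gives 75% to 94%. The documents do not support that: SES and discrimination enter every analysis, so no planned model has 8 df with 10 completers. The manipulation ANCOVA reaches 13 − 5 = 8 df only if all 13 complete, and the extra 3 are there to cover attrition.

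**Conclusion.** The point holds as a minor, cheap improvement. Holm keeps the same 5% family-wise control and never rejects fewer hypotheses. Its benefit is confined to trials in which at least one p-value is at or below .00417. It is negligible at 1 SD, a few points to about 8 points at 2 SD in the 5- and 6-df models, large only at about 3 SD on all 12 outcomes, and near nil for the interaction.

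These sizes rest on assumed effects, correlation 0.3, 10 completers, 1 df per covariate and near-balanced cells. The ordering of the two methods rests on none of these.

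A reader might infer that the Bonferroni level is a mistake, or that Holm would rescue the study's power. Neither follows. The level is correct, and the chance of finding anything at all is the same under both rules.

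**What to change.** In the Data Analysis part of Section 6:

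1. List the 12 tests by outcome and contrast.
2. State whether the ANCOVA tests (manipulation effect and interaction) belong to those 12 or form a separately named family. If separate, say that 5% control applies within each family and not across both.
3. Replace the fixed .004 in both sentences by Holm's step-down at family-wise .05 within the named family, and report Holm-adjusted p-values.

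Step 1 has to come first, because Holm cannot be run on an undefined family. The cost is the list plus two edited sentences; the method is a standard option in SAS and R, which the plan already names. The downside is that simultaneous confidence intervals do not follow directly from Holm. Bonferroni-level intervals (1 − .05/12, or 99.58%) can be reported alongside, with a note that they may include the null for an outcome that Holm rejects.

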## 7. Possible Discomforts and Risks:

### Potential Risks:

While generally safe, the experimental pain procedures confer some limited risks. One risk common to all procedures is that the participant will experience pain or discomfort. Specific risks of each procedure are discussed below.

**Pressure Pain Procedure:** There is a slight chance that a bruise may form as a result of the pressure pain procedure. Also, some patients may experience after-sensations after application of pressure stimuli to their symptomatic knee, though this is expected to be brief in duration. Also, this risk is diminished by applying brief stimuli well below the participant's tolerance level.

**Magnetic Resonance Imaging (MRI):** MRI scanning does not expose subjects to any physical risks by itself. All subjects will be carefully screened for the presence of magnetic material or devices, like pacemakers, etc. that could pose a risk for injury in the MRI scanner. They will

only be allowed into the magnet if magnetic or electronic items can be removed prior to scanning. Some subjects who experience fear of enclosed spaces (i.e. claustrophobia) may not be able to undergo brain MRI scanning. Participants will also be carefully screened for claustrophobia before conducting fMRI scanning.

#### Protections Against Risk:

The experimental pain procedures described in this application are widely used and safe procedures. While they produce pain, risk to the subject is minimal, because: 1) the pain is transient in nature, and generally subsides immediately after the procedure; 2) subjects are instructed that they may stop any procedure at any time with no adverse consequences; and 3) the level of pain experienced by subjects is below their tolerance level. Also, risks will be minimized by adhering to our exclusion criteria. Specific protections included in each procedure are discussed below.

*Pressure Pain Procedure:* The risks of bruising and lingering pain will be diminished by applying brief stimuli well below the participant's tolerance level.

*MRI Procedures:* The primary risk of MRI involves scanning in the presence of magnetic implants or material attached to the participant. Also, claustrophobic responses can be another risk. These risks will be minimized through careful screening of participants, both over the phone and again in-person prior to the imaging procedure. Also, participants will be informed that they can discontinue the procedure at any time should they become uncomfortable. Our team will observe the following procedures to reduce risks associated with the MRI protocol.

#### MRI Pre-Scan Procedures

All subjects in our study will be screened for standard MRI contraindications, including but not limited to:

- The presence non-removable ferrous metal objects
- Aneurysm clips
- Pacemakers
- Other contraindications such as defibrillators, etc.
- Claustrophobia or other subjective discomfort in the scanning environment

#### Subject Positioning:

Proper patient positioning is a key aspect for a successful and comfortable MRI exam. All subjects will be positioned in the same manner for MRI scanning. As a key component of our MRI scanning quality control to insure consistent and safe imaging of the brain, the following patient positioning procedure has been established:

1. Place clean sheet on scanner table and coil cradle.
2. Remove all upper body clothing with metallic trim, such as zippers, buttons or embroideries that may cause artifacts in the MRI images.
3. Provide each patient with ear protection (ear plugs and a headset).
4. Position the patient so the head and neck are relaxed, but without rotation in either plane. The patient should also be well supported in the head coil to maximize comfort and minimize movement.
5. Pillows are placed under the legs to help to decrease strain on the knees as well as assisting in the stabilization of motion in the lower body.
6. Once the patient has been positioned, place sponges along the sides of head for stabilizing support and reduction of motion.

7. Align the centering crosshairs on the patient's nasion (directly between the eyebrows) at every scanning session.
8. Center the head coil over the patients' head, making sure that the patient is high enough in the coil to ensure there is no drop off at the inferior aspect of the brain.
9. The subject is given an alarm ball, and instructed to squeeze the alarm ball in case he/she wants to have the scanning discontinued or needs to initiate communication with the operator of the scanner.
10. The subject is reminded to hold as still as possible and is then advanced to the iso-center of the scanning bore.

These procedures ensure maximum patient safety and comfort while allowing successful and reliable imaging of the brain.

#### **8. Possible Benefits:**

These risks are small relative to the potential benefits to be realized from conducting this research. While participants will not directly benefit from this research, it is hoped that the information to be gained will benefit society by providing new information regarding the neural factors by which pain catastrophizing influence pain and the underlying ethnic group differences in pain and disability.

#### **9. DSMP (Data and Safety Monitoring Plan):**

The current study is not a Phase III clinical trial nor does not involve multiple field sites. However, the current study involves greater than minimal risk, therefore, a formal data safety and monitoring board will not be required. In order to ensure data integrity and safety of human subjects, all adverse events will be reported to both the IRBs and the General Clinical Research Center for their external review. Any subsequent recommendations regarding protocol changes will be implemented. In addition, the PI ([name]) will review the reported adverse events every three months and will conduct interim data analyses to minimize the risk to the study subjects.

#### **10. Conflict of Interest:**

The PI ([name]) has no conflict of interest to disclose.

